5.4.1 Total measurable disease burden

In iRECIST, target and new measurable lesions are used to evaluate the total measurable tumor burden (TMTB). TMTB is the sum of diameters (SOD) of all target and new measurable lesions. Similar to RECIST v1.1, where SOD of the target lesions is used for determination of target lesion response, for iRECIST TMTB is used for determination of target and new measurable lesion response.

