14.3.2.1 Confirming progression

iRECIST defines iUPD (i.e. unconfirmed progression) based on RECIST 1.1 principles. However, unlike RECIST 1.1, iRECIST requires the confirmation of progression (iCPD). Confirmatory scans should be performed at least 4 weeks, but no longer than 8 weeks after iUPD.

iCPD is confirmed if further increase in tumor burden, compared to the last assessment, is evident by one or more of the following:

- Continued increase in tumor burden (from iUPD) where RECIST 1.1 definitions of progression had been met (from nadir) in target, non-target disease or new lesions
 - Progression in target disease worsens with an increase of at least 5 mm in the absolute value of the sum
 - Continued unequivocal progression in non-target disease with an **increase** in tumor burden
 - **Increase** in size of previously identified new lesion (s) (an increase of at least 5 mm in the absolute value of the sum of those considered to be target new lesions) or additional new lesions.
- RECIST 1.1 criteria are met in lesion types (target or non-target or new lesions) where progression was **not** previously identified, including the appearance of additional new lesions.

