14.3.2.2 Assessments following unconfirmed progression (iUPD)

If iUPD is not confirmed at the next assessment, but instead tumor shrinkage (compared to baseline) occurs then an overall response of iCR, iPR or iSD may be assigned as appropriate. Note that new lesions do not need to resolve for iSD or iPR to follow iUPD, provided an increase in size or number of new lesions does not lead to iCPD.

Following iCR, iPR, or iSD the bar is reset so that iUPD must occur again (compared to nadir values) and then be confirmed (by further growth) at the next assessment for iCPD (confirmed progression) to be assigned.

If there is no change in tumor size/extent from iUPD, then the response assessment would again be iUPD.

As can be seen in [Table 14-8](#), the prior documentation of iUPD does not preclude assigning iCR, iPR, or iSD in subsequent assessments providing that iCPD is not documented at the next assessment after iUPD. This approach allows atypical responses, such as delayed responses that occur after pseudoprogression, to be identified, further understood and better characterized.

[figure not shown]

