14.3.2.3 New lesions

New lesions should be assessed and measured as they appear using RECIST 1.1 criteria, and recorded as New Lesions-Target (NLT) or New Lesion-Non-Target (NLNT) to allow clear differentiation from baseline target and non-target lesions. A maximum of 5 NLT may be recorded, no more than 2 per organ, at least 10 mm in long axis (or 15 mm in short axis for nodal lesions).

New lesions may either meet the criteria of NLT or NLNT to drive iUPD (or iCPD). However, the measurements of NLTs should not be included in the sum of measures (SOM) of original target lesions identified at baseline. These measurements will be collected on a separate case report form (CRF).

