2.6 Analysis supporting secondary objectives

2.6.1 Efficacy objectives

The secondary objective is to assess the efficacy of NIR178 in combination of PDR001 using ORR per iRECIST, and other efficacy measures including disease control rate (DCR), duration of response (DOR), progression free survival (PFS) and 2 year overall survival (OS) by both RECIST v1.1 and iRECIST for solid tumors, by PCWG3 guidance (see Protocol Appendix 5) for mCRPC, and by [Cheson et al \(2014\)](#) for DLBCL.

These efficacy endpoints will be summarized for all the treatment groups contributing to the analysis of primary efficacy objective (see [Section 2.1](#) general analysis conventions).

ORR:

Overall response rate (ORR) is defined as the proportion of patients with best overall response (BOR) of immuno-related complete response (iCR) or immuno-related partial response (iPR), as per local review and according to iRECIST (see Protocol Appendix 3 for details) for solid tumors.

ORR as per iRECIST will be provided for each treatment indication along with corresponding 95% confidence interval (CI).

DCR:

DCR is the proportion of patients with a best overall response of CR, PR or stable disease (SD). DCR will be summarized by treatment indication with accompanying 95% confidence intervals.

OS, PFS and DOR:

OS is defined as the time from date of start of treatment to date of death due to any cause. If a patient is not known to have died, OS time will be censored at the date of last contact. The 2 year OS rate is the proportion of patients with at least 2 years of OS.

PFS is defined as the time from start of treatment date to date of the first documented disease progression or date of death, whichever happens first. If a patient has not had the event at the date of analysis cut-off, PFS will be censored at the time of the adequate tumor assessment before the cut-off.

For patients with a confirmed CR or confirmed PR, the DoR is the time from date of first documented response (CR or PR) to date of first documented progression or death due to underlying cancer, whichever happens first. If progression or death has not occurred at the date of analysis cut-off, then DoR will be censored at the date of last adequate tumor assessment before the cut-off.

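### SAP 5.4.1 scores iRECIST response on a sum that includes new lesions, which Protocol Appendix 3 excludes; if that sum is used, secondary iRECIST endpoints can be misclassified in either direction

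*SAP*

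**What the plan says.** SAP 5.4.1 defines total measurable tumor burden (TMTB) for iRECIST: "TMTB is the sum of diameters (SOD) of all target and new measurable lesions". By analogy with the way RECIST v1.1 uses the target sum, it adds that "for iRECIST TMTB is used for determination of target and new measurable lesion response". SAP 5.4.1.1 defines best percentage change on the same total.

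Protocol Appendix 3 says otherwise. On new target lesions (NLT), section 14.3.2.3 states that "the measurements of NLTs should not be included in the sum of measures (SOM) of original target lesions identified at baseline"; they are collected on a separate form. Under the same section and Table 14-8, a new lesion, target or non-target, can produce unconfirmed progression (iUPD) by itself. Section 14.3.2.1 gives the new-lesion growth that confirms progression: "an increase of at least 5 mm in the absolute value of the sum of those considered to be target new lesions". Section 14.3.2.2 adds that "new lesions do not need to resolve for iSD or iPR to follow iUPD", provided the new lesions do not grow or multiply enough to confirm progression.

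SAP 2.6.1 defines iRECIST ORR "as per local review and according to iRECIST (see Protocol Appendix 3 for details) for solid tumors". SAP section 4, which lists changes to protocol-specified analyses, does not mention TMTB.

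**The concern.** The two documents give incompatible instructions for the same visit. A single pooled sum cannot reproduce a scheme in which the target sum and the new lesions are judged separately and by different criteria. The endpoints exposed are the secondary iRECIST ones in solid tumors: ORR, DCR, DoR and PFS. iRECIST is there to identify responses after pseudoprogression, and patients with new lesions are the ones for whom the two rules can disagree. Because SAP section 4 is silent, a reader of the study report would assume that Appendix 3 had been applied.

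**Working it through.** **Inputs.** Cut-offs from Protocol Table 14-3: PR is a fall of at least 30% from the baseline sum; PD is a rise of at least 20% and at least 5 mm from nadir. Smallest non-nodal NLT, 10 mm (14.3.2.3). NLT growth that confirms progression, at least 5 mm (14.3.2.1). Lesion sizes below are illustrative assumptions, with a baseline target sum of 100 mm and scans at least 4 weeks apart.

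**Check on the protocol's own example (14.2.17).** Baseline 200 mm, then 140, 150, 140, 160, 160 mm.
- 140/200 is −30%: PR.
- 150/200 is −25%, and 10/140 = +7.1% from nadir: SD.
- 140 again: PR, now confirmed.
- 160 is 20/140 = +14.3% from nadir, so not PD: PR is carried forward at both visits.

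This gives PR-SD-PR-PR-PR, as the protocol states.

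**The same scans under both rules** (cut-offs applied to TMTB by assumption).

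| Case | Targets (mm) | New lesions (mm) | Appendix 3 | TMTB (mm) | TMTB result |
|---|---|---|---|---|---|
| A | 100/65/60 | 25/20/20 | iUPD-iPR-iPR | 125/85/80 | iPD-iSD-iSD |
| B | 100/100/100 | 10/15/19 | iUPD, then iCPD | 110/115/119 | iSD-iSD-iSD |
| C | 60/60/60 | 0/10/16 | iPR-iUPD-iCPD | 60/70/76 | iPR-iPR-iPD |

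- A, lost responder: targets fall 35% and 40% while the new lesions do not grow, a confirmed iPR. TMTB is +25%, −15% and −20% from baseline, so never iPR.
- B, missed progression: the NLT sum grows 15 − 10 = 5 mm at the second scan, which confirms progression. TMTB is +10%, +15% and +19%, never 20%.
- C, gained responder: under Appendix 3 the first iPR is followed by iUPD, so it stays unconfirmed (14.3.2.4), and NLT growth of 16 − 10 = 6 mm then confirms progression. TMTB of 70 mm is exactly −30% from baseline and 10/60 = +16.7% from nadir, so a second iPR confirms the first under SAP 5.4.3. TMTB of 76 mm is 16/60 = +26.7%, so iPD comes one visit late.

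**Range affected.** Let s be target shrinkage and b the new-lesion burden, both as fractions of the baseline sum. TMTB gives iPR when (1 − s) + b ≤ 0.70, that is s ≥ 0.30 + b. An iPR that Appendix 3 allows is lost when 0.30 ≤ s < 0.30 + b. For b = 15% the required shrinkage is 45%; for b = 30% it is 60%.

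For one 10 mm new lesion:

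| Sum (mm) | iPR lost when target/baseline lies between | Rise on a stable sum |
|---|---|---|
| 50 | 0.50 and 0.70 | 20% (iPD) |
| 100 | 0.60 and 0.70 | 10% (not iPD) |
| 200 | 0.65 and 0.70 | 5% (not iPD) |

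A minimum-size new lesion therefore fails to register as progression whenever the stable nadir sum exceeds 10/0.20 = 50 mm.

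**Best percentage change.** In case A it is −20% on TMTB (80 mm) and −40% on baseline targets (60 mm).

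**Effect of one patient on ORR.** 1/30 = 3.3 points; 1/10 = 10 points.

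**The case against.** The strongest defence is that TMTB may never reach the endpoints. SAP 2.6.1 specifies local review under Appendix 3, SAP 1.1 says the investigator performs all disease assessments, and SAP 5.4.2 to 5.4.4 take visit-level responses as inputs. If those inputs are the investigator's calls, ORR, DCR, DoR and PFS do not move and only best percentage change does. This stands as a condition on the consequence. It does not remove the conflict: SAP 5.4 is presented as the derivation rules for iRECIST, 5.4.1 says TMTB determines response, and Protocol 14.2.17 leaves open whether an investigator or a calculated response is used.

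It also stands that SAP 5.4.1 gives no cut-offs for TMTB and does not expressly withdraw the new-lesion column of Table 14-8. Applying 30% and 20%/5 mm is the natural reading of its analogy with RECIST v1.1, but it remains an assumption. If other cut-offs are meant, they are missing.

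Two stronger readings are tempting. A reader might infer that iRECIST responses are systematically under-counted; case C shows the opposite error, and the documents do not settle the net direction. A reader might also infer that every visit with a measurable new lesion is reclassified. It is not: with b = 15%, targets down 50% give TMTB −35%, an iPR under either rule once Appendix 3 permits response, and targets already at PD are progression both ways.

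Finally, the primary ORR and the Part 1 success and futility rules do not use iRECIST. That limits the weight of the point.

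**Conclusion.** The contradiction between SAP 5.4.1 and both Appendix 3 and SAP 2.6.1 is certain from the text, and it is undeclared. Its effect on iRECIST ORR, DCR, DoR and PFS is conditional on the programmed TMTB response being used and on the RECIST 1.1 cut-offs being applied to it. Under those conditions the errors run in both directions and fall only on patients with measurable new lesions in the ranges shown, so the result cannot be defended as conservative. The documents do not give the number of such patients, so the total effect cannot be sized beyond the per-patient figures. Best percentage change in TMTB mixes target and new lesions whichever visit response governs. The matter should be corrected, but it does not touch the primary analysis.

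**What to change.** In SAP 5.4.1:
- Derive target response from the sum of the baseline target lesions only.
- Let the first appearance of a new lesion, target or non-target, give iUPD.
- Track new target and non-target lesions separately. Confirm progression on growth of at least 5 mm in the NLT sum, any increase in new non-target lesions, or an increase in number.
- State explicitly, following 14.3.2.2, that iSD or iPR may follow iUPD while new lesions persist without such an increase. A bare reference to Table 14-8 is not enough: its last row keeps a patient with a new lesion and prior iUPD at iUPD, and could be read to block the very responses that 14.3.2.2 allows.

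State whether the investigator's or the calculated visit response governs the iRECIST endpoints. Keep TMTB, including 5.4.1.1, only as a labelled exploratory summary. If the sponsor prefers to retain TMTB for response, it should be declared and justified in SAP section 4 with its cut-offs.

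The cost is SAP wording and a change to the iRECIST derivation program, with visit response, BOR, PFS and DoR re-derived where the calculated response is used. New-lesion measurements are already planned on a separate form, so no new data are needed.

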5.4.1.1 Best percentage change from baseline in TMTB

Best percentage change from baseline in TMTB is defined as the percentage change from baseline to the smallest measured post-baseline TMTB occurring at or before the time of confirmed iPD.

5.4.2 Assessment of disease progression

To facilitate analysis, each assessment of progression is categorized as one of three types: pseudo-progression, confirmed progression, and unconfirmed progression.

5.4.2.1 Pseudo-progression

Patients with a single iPD, followed by an assessment of iSD or better will be considered to have a pseudo-progression (pPD). For the analysis purposes, pseudo-progressions are not treated as progression events.

5.4.2.2 Confirmed progression

Confirmed progression 1 (type 1, iCPD1) is declared if a patient has 2 consecutive tumor assessments at least 4 weeks (28 days) apart, both showing disease progression. Assessments with

an iUNK response or iPD assessments <28 days after initial iPD, are discarded. The first iPD is flagged as iCPD1, while all subsequent iPDs are flagged as iXPD1.

The table below shows two hypothetical data scenarios and programming instructions.

Sequence of assessments	Instructions
1 iPD 2 iUNK 3 iPD (Assessment 1 + 30 days)	
 Assessment 3 is ≥ 28 days after Assessment 1 Assessment 3 represents confirmation of iPD at assessment 1 Assessment 1 iPD is flagged iCPD1 Assessment 3 iPD is flagged iXPD1
1 iSD 2 iPD 3 iPD (Assessment 2 + 20 days) 4 iPD (Assessment 2 + 30 days)	
 Assessment 3 is <28 days after Assessment 2 Assessment 4 is ≥ 28 days after Assessment 2 Assessment 4 represents confirmation of iPD at assessment 2 Assessment 2 iPD is flagged iCPD1 Assessment 3 and 4 iPDs are flagged iXPD1

Confirmed progression 2 (type 2, iCPD2) is declared if a patient discontinues treatment following a single iPD with no subsequent assessments ≥ 28 days later. Assessments with an iUNK response or iPD assessments <4 weeks (28 days) after initial iPD, are discarded. Discontinuation of treatment is obtained from EOT eCRF.

The assessment is flagged as iCPD2 and subsequent iPDs (<28 days after first iPD) are flagged as iXPD2.

The table below shows two hypothetical data scenarios and programming instructions.

Sequence of assessments	Instructions
1 iSD 2 iPD - EOT	
 Patient withdraws after initial progression (Assessment 2) without confirmation Assessment 2 iPD is flagged as iCPD2
1 iPD 2 iPD (Assessment 1 + 20 days) - EOT	
 Assessment 2 iPD is <28 days after Assessment 1, so it does not represent confirmation However, patient has completed treatment Assessment 1 iPD is flagged iCPD2 Assessment 2 iPD is flagged iXPD2

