Clinical experience indicates that objective responses to immunotherapy follows delayed kinetics of weeks or months, and can be preceded by initial apparent radiological progression or appearance of new lesions or some enlarging lesions while other target lesions are regressing ("mixed response") ([Wolchok et al 2009](#)). It is therefore reasonable to allow for these possibilities and continue to treat the patient until progression is confirmed and found to be advancing at the next imaging assessment as per iRECIST. An outline of the iRECIST is provided in [Appendix 3](#).

These considerations should be balanced by clinical judgment as to whether the patient is clinically deteriorating and unlikely to receive any benefit from continued treatment.

Such deterioration will be assessed to have occurred after a clinical event that, in the Investigator's opinion, is attributable to disease progression, is unlikely to reverse with continued study treatment and therefore indicates that the patient is not benefiting from study treatment and cannot be managed by the addition of supportive care.

During the treatment period, the patient is obliged to follow the investigators instructions with regards to contraception, concomitant medications and dosing regimen. There is no fixed duration; patients may continue treatment with the study drug until the development of an unacceptable toxicity that precludes any further treatment, disease progression, and /or treatment is discontinued at the discretion of the Investigator or by patient refusal. For details of assessments during the treatment period, refer to [Table 7-1](#), [Table 7-2](#) and [Table 7-3](#).

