7.1.6 Follow-up for disease progression

Patients who discontinue study treatment for any reason other than death, disease progression per confirmed iRECIST ([Appendix 3](#)) or [Cheson et al \(2014\)](#) for DLBCL and/or progressive disease per PCWG3 guidance ([Appendix 5](#)) for mCRPC while on treatment, clinical deterioration or clinical progression, lost to follow-up, consent withdrawal or study termination, also should return for tumor evaluation assessments every 8 weeks (+/- 7 days) during the first 40 weeks, and every 12 weeks (+/- 7 days) thereafter until disease progression, death, loss to follow-up or withdrawal of consent, whichever occurs first. Any newly started antineoplastic therapies during the follow-up period must be recorded on the Antineoplastic therapy since discontinuation eCRF. Once patient starts on new antineoplastic therapy post discontinuation of study treatment, patient does not need to be followed for disease progression.

If patients refuse to return for these visits or are unable to do so, every effort should be made to contact them or a knowledgeable informant by telephone to determine if the patient had disease progression. Once the Follow up for Disease progression period ended, the End of Post treatment Phase disposition eCRF should be completed.

Antineoplastic therapies or tumor directed surgical procedures initiated during the disease progression follow-up period must be recorded on the Antineoplastic therapies since discontinuation of study drug eCRF.

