Imaging assessments as described in [Table 7-4](#) should be performed at the time points specified using the same imaging modality used at baseline, irrespective of study treatment interruption or actual dosing (see [Table 7-1](#), [Table 7-2](#) and [Table 7-3](#)). Imaging assessments for response evaluation will be performed every 8 weeks (+/- 7 days) during the first 40 weeks, and every 12 weeks (+/- 7 days) thereafter until disease progression, death, lost to follow-up or withdrawal of consent or patient starts new antineoplastic therapy post discontinuation of study treatment.

Imaging assessments should be scheduled using the randomization date as the reference date (not the date of the previous tumor assessment), and should be respected regardless of whether treatment with study treatment is temporarily withheld or unscheduled assessments performed.

Additional imaging assessments may be performed at any time during the study at the investigator's discretion to support the efficacy evaluations for a subject, as necessary. Clinical suspicion of disease progression at any time requires a physical examination and imaging assessments to be performed promptly rather than waiting for the next scheduled imaging assessment.

Each lesion that is measured at baseline must be measured by the same method (either same imaging method or by photography, including a metric ruler) and when possible, the same local radiologist/physician throughout the study so that the comparison is consistent. If an off-schedule imaging assessment is performed because progression is suspected, subsequent imaging assessments should be performed in accordance with the original imaging schedule.

Combined PET/CT may be used only if the CT is of similar diagnostic quality as a CT performed without PET, including the utilization of IV contrast media. At the discretion of the Investigators, FDG-PET scans may be performed to document progressive disease per RECIST 1.1 ([Appendix 2](#)).

If a patient has a PR or CR, the result will be confirmed by a new assessment after at least 4 weeks.

If a solid tumor patient has progressive disease, as per iRECIST, the result will be confirmed after at least 4 weeks.

Similarly, if a lymphoma patient has progressive disease, the result will be confirmed after at least 4 weeks per [Cheson et al \(2014\)](#) criteria.

For mCRPC, efficacy will be evaluated using RECIST 1.1, iRECIST and PCWG3 guidance ([Appendix 5](#)).

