14.3.2.5 Examples of iResponse assignment

Table 14-8 Time Point (TP) iResponse

Target Lesions*	Non-Target Lesions*	New Lesions*	Time Point Response	
			No prior iUPD*	Prior iUPD**, ***
iCR	iCR	No	iCR	iCR
iCR	Non-iCR/ Non-iPD	No	iPR	iPR
iPR	Non-iCR/ Non-iUPD	No	iPR	iPR
iSD	Non-iCR/ Non-iUPD	No	iSD	iSD
iUPD with no change OR decrease from last TP	iUPD with no change OR decrease from last TP	Yes	NA	NLs confirms iCPD if NLs were previously identified and increase in size (≥5mm in SOM for NLT or any increase for NLNT) or number. If no change in NLs (size or number) from last TP, remains iUPD.
iSD, iPR, iCR	iUPD	No	iUPD	Remains iUPD unless iCPD confirmed based on further increase in size of NT disease (need not meet RECIST 1.1 criteria for unequivocal PD)
iUPD	Non-iCR/Non-iUPD	No	iUPD	Remains iUPD unless iCPD confirmed based on further increase in SOM of at least 5mm
iUPD	iUPD	No	iUPD	Remains iUPD unless iCPD confirmed based on further increase in: 
 • Previously identified T lesion iUPD SOM ≥5mm and/or • NT lesion iUPD (prior assessment – need not be unequivocal progression)
iUPD	iUPD	Yes	iUPD	Remains iUPD unless iCPD confirmed based on further increase in: 
 • Previously identified T lesions iUPD ≥5mm and/or • Previously identified NT lesion iUPD (need not be unequivocal) and/or • Size or number of new lesions previously identified
Non-iUPD/PD	Non-iUPD/PD	Yes	iUPD	Remains iUPD unless iCPD confirmed based on 
 • Increase in size or number of new lesions previously identified

* Using RECIST 1.1 principles. If no pseudoprogression occurs, RECIST 1.1 and iRECIST categories for CR, PR and SD would be the same.

** in any lesion category.

*** identified in the assessment immediately prior to this assessment.

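### SAP 5.4.2.2 confirms iRECIST progression without the further growth that Protocol Appendix 3 requires, so secondary iRECIST results can change for patients who later recover

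*SAP*

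**What the plan says.** **SAP.** Section 2.6.1 defines iRECIST ORR by local review with reference to Protocol Appendix 3, and also reports DCR, DoR and PFS by iRECIST. Section 5.4.2.2 then gives the programming rule: iCPD1 "is declared if a patient has 2 consecutive tumor assessments at least 4 weeks (28 days) apart, both showing disease progression". Its worked examples check only the interval. Section 5.4.2.1 treats one progression scan followed by stable disease or better as pseudo-progression. Section 5.4.3 closes best response at the first flagged progression, and 5.4.4.1 dates the event there.

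**Protocol Appendix 3.** Section 14.3.2.1 states that "iCPD is confirmed if further increase in tumor burden, compared to the last assessment, is evident by one or more of the following". The list covers:
- at least 5 mm more in the target sum;
- at least 5 mm more in the sum of new target lesions;
- continued non-target progression with increased burden;
- additional new lesions;
- progression in a lesion type not previously progressing.

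Table 14-8 gives the target-lesion case: "Remains iUPD unless iCPD confirmed based on further increase in SOM of at least 5mm". Section 14.3.2.2 covers a flat scan: "If there is no change in tumor size/extent from iUPD, then the response assessment would again be iUPD". It adds that "the prior documentation of iUPD does not preclude assigning iCR, iPR, or iSD in subsequent assessments providing that iCPD is not documented"; the condition refers to the scan straight after iUPD.

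**Protocol body.** Section 7.1.2 speaks of continuing to "continue to treat the patient until progression is confirmed and found to be advancing at the next imaging assessment as per iRECIST". Section 7.2.1 says only that iRECIST progression is confirmed after at least 4 weeks.

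**The concern.** The SAP points to Appendix 3 for the criterion but programs a different definition of confirmation. The 28-day interval cannot stand in for growth, because scheduled scans are already further apart than that. Any second scheduled scan still at progression level therefore confirms, even if the tumor has shrunk since the first.

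No other SAP category catches these patients. Pseudo-progression in 5.4.2.1, iCPD2 in 5.4.2.2 and unconfirmed progression in 5.4.2.3 are all worded for a single progression scan, so Appendix 3's repeated iUPD has no place. Yet the protocol leaves room for the pattern: 6.1.3 anticipates late responses and prolonged tumor flare, and 7.1.6 continues tumor assessment for "Patients who discontinue study treatment for any reason other than death, disease progression per confirmed iRECIST" and the other listed reasons. At stake is whether a delayed response after a flat period of apparent progression is counted as a response or as an early progression event.

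**Working it through.** The plan gives no figure that depends on this rule, so the check applies both rules to the same scans.

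**Inputs.** Progression is at least 20% and at least 5 mm above the smallest sum, and partial response is at least 30% below baseline (Protocol Table 14-3). Scans: "Imaging assessments for response evaluation will be performed every 8 weeks (+/- 7 days) during the first 40 weeks", then every 12 weeks. The best-response hierarchy is from SAP 5.4.3. Time to event is end date minus start date plus 1 (Protocol 14.2.34). Only target lesions are modeled. A run of progression scans that never recovers counts as an event at its first scan under both rules.

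**Interval.** With one scan 7 days late and the next 7 days early, the gap is 56 − 14 = 42 days (84 − 14 = 70 days after week 40). Both exceed 28 days.

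**Examples** (sums in mm, baseline first; scans at weeks 8, 16, 24, 32, 40, 52):

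| Sums | Appendix 3 | SAP |
|---|---|---|
| A: 100/125/126/65/65 | confirmed iPR, no event | iPD, event at week 8 |
| B: 100/125/126/95/95 | iSD, no event | iPD, event at week 8 |
| C: 100/65/65/80/81/64/64 | iPR, response ongoing at week 52 | iPR, response ends at week 24 |
| D: 100/125/120/65/65 | confirmed iPR, no event | iPD, event at week 8 |
| No recovery: 100/125/126/126 | iPD, event at week 8 | same |
| Qualifying growth: 100/125/131/65/65 | iPD, event at week 8 | same |
| Single progression: 100/125/95/95 | iSD, no event | same |

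In A the second scan adds 126 − 125 = 1 mm, short of 5 mm. In D it has shrunk by 5 mm but is still 20% above the smallest sum. In C, DoR is (24 − 8) × 7 + 1 = 113 days under the SAP and at least (52 − 8) × 7 + 1 = 309 days under Appendix 3.

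**Grid.** All 25⁴ = 390,625 sequences of four sums from 40 to 160 mm in 5 mm steps, baseline 100, were run. The rules differed in 35,595:
- best response changed from iPD (SAP) to iSD (Appendix 3) in 19,020;
- best response changed from iPD to iPR in 1,620;
- only the event changed in 14,955.

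None differed without later recovery. All 19,020 + 1,620 = 20,640 best-response changes had progression at the first scan. These are counts of possible patterns, not frequencies.

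**Disease control.** The first scan falls at day 56 ± 7, so no earlier than day 49, beyond the 42 days that SAP 5.4.3 requires for iSD. Stable disease or better at that scan already secures iSD, so disease control is lost only when the first evaluable scan is progression. A response can be lost more widely. In 100/95/120/121/65/65, week 16 is 25 mm (26%) above the smallest sum and week 24 adds 1 mm; best response is iSD under the SAP and iPR under Appendix 3. The four-scan grid is too short to contain that pattern.

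**Size per patient.** 1/30 = 3.3 points, 1/20 = 5 points, 1/10 = 10 points of a group's iRECIST ORR.

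**The case against.** The case for leaving the rule alone has substance.

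- **The SAP states its rule openly.** Protocol 14.2.29, in the RECIST appendix, accepts deviations defined in the SAP. The Appendix 3 citation in SAP 2.6.1 attaches to ORR only, while 5.4.4 gives its own rules for time-to-event endpoints. This stands, and makes the omission from SAP Section 4 a labeling gap. It does not remove the conflict for ORR, where the SAP cites one criterion and programs another.
- **The protocol body is mixed.** Section 7.1.2 supports growth, but 7.2.1 gives only a 4-week interval. A reader might infer that the whole protocol insists on growth, or that 7.2.1 licenses the SAP rule. Neither follows: 7.2.1 refers to iRECIST, and Appendix 3 is where the protocol defines it.
- **The effect is narrow.** DCR, DoR and PFS are also reported by RECIST 1.1, and the study closed for insufficient efficacy. This stands and limits the severity.
- **A careless repair would do harm.** If growth were required but the SAP's single-progression wording kept, 100/125/126/126 followed by end of treatment would fit no category: not iCPD1 (no growth), not iCPD2 (a later scan at least 28 days on exists), not ongoing, not pseudo-progression. It would lose its event. On the grid, 57,435 sequences end in such a run, more patterns than the 35,595 being repaired. This stands and shapes the fix.

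**Conclusion.** The conflict is real but minor. SAP 5.4.2.2 and Appendix 3 give different secondary iRECIST results only for a patient with two or more progression scans, no qualifying growth, and later recovery to stable disease or better. No frequency can be derived from the documents, and the pattern is probably uncommon.

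Three stronger readings are tempting but unsupported.
- **That efficacy decisions are affected.** The primary ORR uses RECIST 1.1, Cheson or PCWG3, so it, futility, the success criteria and OS do not depend on this rule.
- **That every patient with a flat second progression scan is misclassified.** Those who never recover keep the same event date, provided such a run is counted as an event at its first scan.
- **That closing best response at confirmed progression breaches Appendix 3.** It does not; only the definition of confirmation conflicts.

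The worked examples assume target lesions only. Non-target and new-lesion routes to confirmation were not modeled.

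**What to change.** **Preferred: align SAP 5.4 with Appendix 3.**
1. Add the further-increase condition of Protocol 14.3.2.1 to iCPD1, applied separately to the baseline target sum and the new-target-lesion sum. First reconcile SAP 5.4.1, which pools target and new measurable lesions into one burden, with Protocol 14.3.2.3, which keeps new lesions out of the target sum. Use the investigator's visit assessment for non-target lesions.
2. Let progression scans without that increase stay iUPD, and leave best response open.
3. Extend pseudo-progression in 5.4.2.1 to one or more consecutive unconfirmed progressions followed by stable disease or better.
4. Rewrite the single-progression wording in the opening of 5.4, in iCPD2 (5.4.2.2) and in 5.4.2.3 to cover one or more consecutive progression assessments without confirmation and without later recovery. Date the event at the first scan of the unbroken run. Then 100/125/126/126 followed by end of treatment keeps its week-8 event. It also settles 100/125/126/133, where the present dating sentence could mean week 8 or week 16, a difference of 56 days.

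**Alternative.** Keep the rule, call it a modified iRECIST criterion, list it in SAP Section 4, and report the Appendix 3 derivation as a sensitivity analysis.

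**Cost.** SAP wording and programming. Target diameters (Protocol 14.2.7) and new-target-lesion measurements (14.3.2.3) are collected, which is enough for the 5 mm tests. Non-target measurements are not required, so check first what the CRF records for them.
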